7.1.2 Assessment Time Windows

All data collected during follow-up will be displayed and analyzed according to the actual visit that the data are assigned in the eCRF.

Study discontinuation visits will be assigned to the corresponding visit if it falls within the protocol window for that visit. For example, a discontinuation visit on day 100 would be assigned to Week 13 since it falls within the -7/+14 day window for Week 13.

However, if scheduled visit data are present, then the discontinuation visit data will not be used for that visit. This will be done on a parameter level and discontinuation visit values will not be assigned to visits where the assessment was not scheduled to be taken (For example, Week 4 does not have MRI, but the discontinuation visit does; even if the discontinuation visit falls in the Week 4 window, we would not assign the MRI findings to a Week 4 visit).

Unscheduled assessments (laboratory data, imaging findings or vital signs associated with non-protocol clinical visits or obtained in investigating or managing AEs) will be included in listings but not summaries of the data. Likewise, discontinuation visit data that do not fall within a protocol-defined window or fall within a window where

scheduled visit data are already present will not be summarized, but will appear in listings.

7.2 Efficacy Variables

The primary efficacy outcome is the change from baseline in the weekly averages of the VAS worst leg pain assessed at Weeks 1, 2, 4, 6, 13, 26, 39, and 52. Baseline is defined as the average of the 7 daily worst pain measures leading up to the randomization visit.

Key secondary outcomes include:

- Change from baseline to Week 13 in herniation volume
- Change from baseline to Week 13 in ODI score
- Change from baseline to Week 52 in average worst leg pain score during the past 24 hours over the previous 7 days, as assessed by 100 mm VAS.

Supportive outcomes include:

- Change from baseline in worst leg pain score at each time point
- Change from baseline in worst back pain score at each time point
- Change from baseline in ODI score at each time point
- Percentage of subjects with negative SLR test at each time point
- Percentage of subjects without hypoesthesia, muscle weakness or hyporeflexia at each time point
- Patient Global Impression of Change (PGIC) score at each time point
- Clinical Global Impression of Change (CGIC) score at each time point
- Change from baseline in SF-36 scores at each time point
- EQ-5D-5L (EuroQol Group 5-Dimension Quality of Life instrument, 5-level version) quality of life (QOL) score and VAS score at Week 13 and Week 52
- WPAI score at Week 13 and Week 52
- Incidence and amount of rescue medication use over 13 weeks
- Change from baseline in amount of rescue medication use at each time point
- Cumulative distribution of percentage change from baseline in worst leg pain score at Week 13 and Week 52
- Cumulative distribution of percentage change from baseline in ODI score at Week 13 and Week 52
- Responder rate by composite definition at Week 13
- Change from baseline in intervertebral disc volume at Week 13 and Week 52
- Change from baseline in herniation volume at Week 13 and Week 52
- Incidence of post-treatment surgery for LDH at the same level of investigational product injection
- Number of subjects with recurrence of LDH at Week 52

7.3 Analysis Methods

7.3.1 Estimand

Population

The analysis population will be mITT subjects (randomized and injected) with LDH as defined by the protocol inclusion/exclusion criteria.

Variable

The primary endpoint will be the change from baseline to Week 13 in the weekly average of daily VAS worst leg pain scores. Three days of non-missing values are required for each weekly average.

Intercurrent Events

Observations following concomitant therapies of lumbar operation, lumbar percutaneous nucleotomy, or lumbar intradiscal therapies will be censored. Otherwise, no special handling will be employed for intercurrent events; once injected it is impossible for the subject to go off treatment and data will be analyzed as observed.

Population-Level Summary

The population-level summary will be the difference in least-square means between treatment arms (analyzed as randomized) at Week 13 from the primary analysis model. See Section [7.3.2](#) below for details.

7.3.2 Primary Efficacy Analyses

The change from baseline in the worst leg pain scores will be analyzed by a mixed model for repeated measures (MMRM) analysis for Week 1 through Week 52 in the mITT population. Records analyzed will be the weekly averages at Weeks 1, 2, 4, 6, 13, 26, 39, and 52 (see Section [7.3.2.1](#) for additional details).

The primary comparison will be the mean change from baseline of the SI-6603 group at Week 13 compared with the control group, estimated using this model. The model will include the baseline worst leg pain score, treatment, time, treatment-by-time interaction, and duration of leg pain as fixed effects.

An unstructured covariance will be used to model the covariance structure among repeated measures. Should the model fail to converge with the type = UN option, a compound symmetry structure will be used. Kenward-Roger method will be used for computing the denominator degrees of freedom. The missing data will be implicitly handled via a mixed-effect model, without explicit imputation.

The primary efficacy objective will be tested using the null hypothesis that there is no difference in the mean change from the pretreatment measure of pain relief (weekly average VAS worst leg pain) between SI-6603 and control at 13 weeks. This null hypothesis can be expressed as the hypothesis test

$H_0: \delta_{13} = 0$ vs. $H_A: \delta_{13} \neq 0$

where δ_{13} is the mean difference in the change from the pretreatment measure of pain relief (weekly average VAS worst leg pain) between SI-6603 and control at Week 13 from the model-based estimates of each treatment's change from pretreatment at those visits.

Worst leg pain score and change from baseline in worst leg pain score will be summarized by treatment group and time point. Mean change from baseline over time will be summarized in a line graph with error bars.

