2.5 Randomization

All eligible subjects will be randomized on a 1:1 basis to SI-6603 or control based on a computer-generated randomization schedule. The randomization will be balanced by randomly permuted blocks and stratified by site.

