2.6 Sample Size Determination

It is planned to enroll approximately 320 subjects, 160 in the SI-6603 group and 160 in the control group.

Sample size estimation is based on using the mean difference in the worst leg pain score change from baseline in the primary efficacy analysis. The following assumptions were made to compute the sample size:

- The 2-sample t-test comparing the group means of the change from baseline was used. (The 2-sample t-test approximates the test of the null hypothesis based on the repeated measures model that will be used in the primary efficacy analysis.)
- Treatment difference between SI-6603 and control groups of 12 mm
- Common standard deviation (SD) of 30 mm
- Dropout rate of 15%
- Power of 90%
- Two-sided significance level of 5%

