5. STUDY SUBJECTS

5.1 Disposition of Subjects

A disposition table of subjects will include the number and percentage of subjects for the following categories: subjects screened, subjects randomized, subjects treated (safety sample), subjects in the mITT sample, subjects in the PP sample, subjects completing through Week 13, subjects completed study, and subjects discontinued from the study. A separate summary of discontinuations through Week 13 will also be presented. All percentages will be based on the number of subjects randomized (with the exception of subjects screened). Additionally, the number of subjects excluded from each population and reason for exclusion will be presented overall and by site.

The reasons for study discontinuation will also be summarized in this table. The reason for discontinuation may include any of the following: lack of efficacy, death, adverse event, lost to follow-up, failure to meet randomization criteria, protocol violation, physician decision, withdrawal by subject, pregnancy, study terminated by sponsor, and other. Subjects that do not complete the study will be flagged if they had early termination due to confirmed COVID-19, early termination at site discretion due to COVID-19, or early termination at subject discretion due to COVID-19; this will be summarized with the number and percentage of subjects in each category. Only the primary reason for study discontinuation will be recorded for a given subject.

The number and percentage of subjects attending each visit will be summarized. Due to the COVID-19 pandemic, visits could be in-person, remote or a combination; the reason for a remote visit could be due to the subject having confirmed COVID-19, at site discretion due to COVID-19, at subject discretion due to COVID-19 or other reasons. Likewise visits may have been missed or canceled due to the subject having confirmed COVID-19, at site discretion due to COVID-19, at subject discretion due to COVID-19 or other reasons. Additionally, individual assessments may have been omitted due to COVID-19; this is recorded on the CRF.

The type of visit (in-person, remote, or combination), the reason for remote visits, the reason visits were missed and assessments missed due to COVID-19 will be summarized with counts and percentages for each visit and treatment group.

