7.3.2.2 Sensitivity analyses

As a sensitivity analysis, missing data for participants in the mITT population will be imputed via MI. Twenty repeats of the imputation will be performed using Markov Chain Monte Carlo (MCMC) assuming non-monotone missing. Where the subject was discontinued due to lack of efficacy, due to an AE (with the exception of COVID-19), the subject has met the criteria for treatment failure as described in Section 7.3.3.4, or the subject's values are censored due to a prohibited therapy as described in Section 7.3.2.1, missing values will be imputed drawing from the baseline values, conditioned on the non-missing post-baseline values, of all participants in the mITT population under the assumption that they are missing not at random (MNAR); duration of leg pain will be included as a covariate.

If the study medication was discontinued for any other reason, values will be imputed within treatment group using MI under the assumption that they are missing at random (MAR) with covariates for duration of leg pain, and the weekly average worst leg pain score recorded at each time point (including baseline). The MAR approach will also be applied for sporadic missing values (prior to discontinuation). Values missing due to COVID-19, whether the result of early termination or sporadic missing values, are assumed MAR and unrelated to the endpoint of the weekly average VAS worst leg pain.

Data will be imputed for the full set of visits as described above and the same output will be used as a sensitivity for both the primary at Week 13 and the secondary endpoint at Week 52.

The MMRM analysis as described for the primary will be repeated for each of the 20 sets of data and combined using SAS PROC MIANALYZE. See Appendix [13.2](#) for the list of random seeds.

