7.3.2.3 Per Protocol Analyses

The primary analysis and the key secondary analyses will be repeated on the PP population.

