7.3.3 Secondary Efficacy Analyses

7.3.3.1 Key Secondary

A longitudinal analysis model will be used as described in the primary efficacy analysis for the analyses of change from baseline in the herniation volume at Week 13, change from baseline in the worst leg pain score at Week 52, and change from baseline in the ODI at Week 13. The baseline value of each outcome will be included as a covariate in these models in place of the baseline worst leg pain score (from the primary analysis). Note that herniation volume is collected only at Weeks 13 and 52; ODI assessment shares the same time points as the primary.

Key secondary endpoints will be summarized by treatment group and time point. Mean change from baseline in key secondary endpoints over time will be summarized in a line

graph with error bars. Estimated value in key secondary endpoints over time will be summarized in a line graph with 95% confidence interval (CI) displayed.

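### Site is the only randomisation stratum but is in no planned model, a small and avoidable loss of power; compound symmetry is also too blunt as the only covariance fallback

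*SAP*

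**What the plan says.** SAP 2.5, in agreement with Protocol 3.7, sets 1:1 allocation and adds: "The randomization will be balanced by randomly permuted blocks and stratified by site". No other stratification factor is named.

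SAP 7.3.2 lists the terms of the primary mixed model: "The model will include the baseline worst leg pain score, treatment, time, treatment-by-time interaction, and duration of leg pain as fixed effects". Protocol 11.6.1 and the synopsis give the same list. Site is absent.

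The other analyses inherit this model:
- Key secondary endpoints (SAP 7.3.3.1): "A longitudinal analysis model will be used as described in the primary efficacy analysis", with only the baseline covariate exchanged.
- Multiple imputation (SAP 7.3.2.2): "The MMRM analysis as described for the primary will be repeated for each of the 20 sets of data". SAP 7.3.3.2 extends this to the key secondary endpoints.
- Per-protocol (SAP 7.3.2.3): "The primary analysis and the key secondary analyses will be repeated on the PP population".
- Subgroups (SAP 7.3.2.4) follow the primary model where possible, and site is not one of the subgroups.

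Outside randomisation, site is used only for a table in SAP 5.1, where "the number of subjects excluded from each population and reason for exclusion will be presented overall and by site". SAP section 11 gives no reason for leaving site out of the models.

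On covariance, SAP 7.3.2 and Protocol 11.6.1 name one alternative to the unstructured matrix: "Should the model fail to converge with the type = UN option, a compound symmetry structure will be used". Neither mentions an intermediate structure or a robust standard error.

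**The concern.** Blocking within site removes most between-site variation from the treatment comparison. A model without site still counts that variation as residual error. If site is prognostic, the reported standard error is therefore larger than the true one, and precision that the design has already secured is not used. Because every supporting analysis repeats the same model, none recovers it.

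The fallback is a separate, conditional matter. Compound symmetry puts one variance and one correlation on eight visits from Week 1 to Week 52. If the spread of pain changes differs between visits, the Week 13 and Week 52 standard errors come from a pooled variance that fits neither. Week 13 is the primary test, and Week 52 leg pain is the first key secondary test in the sequence of SAP 7.3.4. A standard error that is too small at either visit raises the chance of a false claim there. Herniation volume and ODI have their own models and keep their own 5% tests unless their unstructured fits also fail.

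**Working it through.** **Inputs.** SAP 2.6 gives a difference of 12 mm, "Common standard deviation (SD) of 30 mm", 15% dropout, 90% power, two-sided 5% and 160 per arm. The documents give no site share of variance (ρ), number of sites, block size or SD by visit, so these are assumed and varied.

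**Step 1: the plan's own figure.** n = 2(1.960 + 1.282)² × 30²/12² gives 132 per arm (133 by exact t-test). Dividing by 0.85 gives 156 (157), against about 160 planned. Evaluable: 160 × 0.85 = 136 per arm. SE = 30√(2/136) = 3.638 mm, and power = Φ(12/3.638 − 1.960) = Φ(1.338) = 91.0%. The stated size reproduces.

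**Step 2: leaving site out, closed form.** With ideal balance within site, the true SE is 3.638√(1 − ρ), while the model without site reports 3.638.
- Excess width = 1/√(1 − ρ) − 1
- Type I error = 2[1 − Φ(1.960/√(1 − ρ))]
- Power without site = Φ((12 − 1.960 × 3.638)/true SE)
- Power with site = Φ(12/true SE − 1.960)

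At ρ = 5% the true SE is 3.546. Power without site is Φ(4.870/3.546) = Φ(1.373) = 91.5%. With site it is Φ(3.384 − 1.960) = Φ(1.424) = 92.3%.

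| Assumed ρ | SE too wide by | Type I error without site | Power without site | Power with site |
|---|---|---|---|---|
| 0% | 0% | 5.0% | 91.0% | 91.0% |
| 2% | 1.0% | 4.8% | 91.2% | 91.5% |
| 5% | 2.6% | 4.4% | 91.5% | 92.3% |
| 10% | 5.4% | 3.9% | 92.1% | 93.5% |
| 20% | 11.8% | 2.8% | 93.3% | 95.8% |

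These losses are upper bounds, because balance within site is never perfect. At 2%, 5% and 10% they are worth about 2, 4 and 8 evaluable subjects per arm.

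**Step 3: simulation of the eight-visit model.** Assumptions: 320 randomised; blocks of 4 within site; SD 30 mm; correlation from 0.84 (adjacent visits) to 0.44 (Week 1 with Week 52); random dropout of 15% by Week 13 and 25% by Week 52; 3% sporadic missing. There were 1,500 runs per scenario, with REML, unstructured covariance and 260 fixed degrees of freedom. The change on adding one random site intercept was:

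| Scenario | SE falls by | Power gain (points) | Type I error, without / with site |
|---|---|---|---|
| 40 uneven sites, no site effect | 0.3% | 0.1 | 5.5 / 5.6% |
| 40 sites, ρ 5%, constant over visits | 2.2% | 0.7 | 5.1 / 5.5% |
| 40 sites, ρ 10%, constant | 4.6% | 1.4 | 4.7 / 5.4% |
| 40 sites, ρ 5%, site effects correlated 0.5 between visits | 1.1% | 0.3 | 5.1 / 5.2% |
| 40 sites, ρ 10%, correlated 0.5 | 2.1% | 0.7 | 4.4 / 4.7% |
| 64 sites of 5, ρ 10%, constant | 4.3% | 1.1 | 4.5 / 5.2% |

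The simulation SE is 0.2 points for the power gain and 0.6 points for type I error. The site variance was estimated at zero in 54% of runs with no site effect, 5% to 15% at ρ = 5%, and 0.4% to 5% at ρ = 10%.

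Unpooled fixed site effects behave differently. In a single-visit simulation with 64 sites of 5, they changed power by −2.9, −1.6 and −0.6 points at ρ = 0, 5% and 10%.

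**Step 4: the fallback.** The unstructured fit converged in all 9,000 trials of step 3 and all 2,100 below. The 95% upper bound on failure is 3/11,100 = 0.03%, though real data may be less regular. Given failure, with 700 runs per assumed SD profile:

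| Assumed SD over visits | Compound symmetry, type I error Week 13 / 52 | Heterogeneous Toeplitz with sandwich SE |
|---|---|---|
| Rising from 15 to 34 mm | 8.7 / 15.3% | 5.3 / 5.3% |
| 30 mm, then 36 mm after Week 13 | 4.0 / 8.9% | 5.4 / 5.1% |
| Falling from 34 to 28 mm | 4.4 / 3.4% | 5.3 / 5.1% |

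Heterogeneous compound symmetry with a sandwich SE gave 4.7% to 4.9%. The simulation SE is about 0.8 points near 5% and 1.4 at 15.3%. Weighted by an assumed failure rate, the worst Week 52 figure is 0.99 × 5 + 0.01 × 15.3 = 5.1% at 1% failure, and 0.95 × 5 + 0.05 × 15.3 = 5.5% at 5%.

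**The case against.** No stated property of the plan fails. Protocol and SAP agree on the model, the estimate is unbiased, the test errs on the conservative side, and power without site is at least 91% in every closed-form case. The gain rests on an assumed site share whose range starts at zero, and 1.4 points needs a 10% share that is constant over a year. All of this stands, and it is why the point is minor.

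Part of the gain is the test moving up from a conservative level. Simulated type I error is higher with site in all six scenarios, averaging 5.3% against 4.9%. Each difference is within simulation error, but Kenward-Roger was not simulated, and no separate convergence rate is available for the model with site. The drop rule below covers non-convergence.

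The fallback point is nearly hypothetical. The 15.3% needs both a failed fit and a steeply rising SD, and another profile is conservative. The proposed list is also only partly tested. Heterogeneous AR(1) was not simulated, and the assumed correlations may favour Toeplitz. Dropout was random, whereas poor responders may be withdrawn (Protocol 5.1). A sandwich standard error does not correct a mean shifted by a wrong covariance; under pain-driven dropout, a large-sample check put the shift for heterogeneous Toeplitz at about 0.4 to 0.5 mm at Week 52. These limits stand, but they do not favour compound symmetry.

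**Conclusion.** The concern holds as a minor point. Leaving out the only stratification factor gives up nothing if site is not prognostic. It gives up roughly 0.3 to 0.8 points of power at a 5% site share and 0.7 to 1.5 at 10%, depending on the number of sites and how stable site effects are over time. It causes no bias, no inflated error and no shortfall against the stated 90%. The absence of site from the models is certain from the text; the size is not, because it depends on a site share and site count that the documents do not give.

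The fallback is a secondary point that matters only if the unstructured fit fails. Its direction and size are then unknown without SDs by visit, and both the primary Week 13 test and the Week 52 test would be affected.

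**What to change.** 1. In SAP 7.3.2 and 7.3.3.1, add site as a random intercept, keeping the unstructured covariance and Kenward-Roger. State that if the site variance is estimated at zero, or the model does not converge, site is dropped and the unstructured covariance is kept. Do not use unpooled fixed site effects. Apply the same rule to the per-protocol, imputation and subgroup fits. If the sponsor prefers no site term, the SAP should say why.
2. Replace the compound-symmetry sentence by an ordered list, fitted without site, taking the first structure that converges: heterogeneous Toeplitz, heterogeneous AR(1), heterogeneous compound symmetry. For these fits use a sandwich standard error with between-within degrees of freedom in place of Kenward-Roger.
3. Record both changes in SAP section 11, or amend Protocol 11.6.1 and the synopsis, before unblinding.

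The cost is a few lines of text and one extra variance parameter. No new data are needed, since site is known for every randomised subject. One limit remains: the imputation step itself would still omit site, so site variance would be slightly understated in those sensitivity analyses.

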1.2.2.1 Improvement of LDH Symptoms

In the Japanese Phase 3 study, statistically significant differences were observed in the Least Squares (LS) mean change from baseline in worst leg pain at Week 13 in the 1.25 U dose group compared with the placebo group (-49.5 mm in 1.25 U group and -34.3 mm in placebo group on a 100 mm visual analogue scale [VAS]). This finding demonstrated the superiority of SI-6603 over placebo for the treatment of LDH in this study. The decrease in mean worst leg pain in the treatment groups also continued beyond Week 13; at the final observation at Week 52, the values were 30.9 mm in the placebo group and 18.5 mm in the 1.25 U dose group on a 100 mm VAS. These results indicated that SI-6603 treatment led to long-term improvement of leg pain due to LDH.

In addition, the LS mean change from baseline in worst low back pain at Week 13 was -28.5 mm in 1.25 U dose group and -21.4 mm in the placebo group. The LS mean change from baseline in worst low back pain at Week 52 was -34.0 mm in 1.25 U dose group and -24.5 mm in placebo group. This difference between treatment groups was not statistically significant, but a similar study by McGirt et al. assessing the VAS scores of 108 lumbar discectomy patients showed that low back pain improved from 4.6 cm before surgery to 2.1 cm at 6 weeks after surgery, which means the change from baseline was -25.0 mm.⁽¹²⁾ These results indicated that the observed improvement in low back pain with SI-6603 injection would be considered clinically beneficial.

1.2.3 Rationale for Study Design, Administration Route, Dosage (Regimen), and Treatment Period Selection

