7.3.4 Multiple Comparisons

To control family-wise error rate for multiple tests of the primary and key secondary endpoints, serial gatekeeping testing algorithm will be used.

1. The treatment effect on the primary endpoint will be evaluated at $\alpha = 0.05$.
2. If the effect on the primary endpoint is significant, the treatment effect on the key secondary endpoint of worst leg pain score at Week 52 will be evaluated using $\alpha = 0.05$.
3. If worst leg pain score at Week 52 is significant $\alpha = 0.05$, then the herniation volume at Week 13 will be tested at $\alpha = 0.05$.
4. If the herniation volume at Week 13 is significant $\alpha = 0.05$, then the ODI at Week 13 will be tested at $\alpha = 0.05$.

If at any point in the sequence an endpoint fails to meet significance at $\alpha = 0.05$, then the algorithm will be halted and the remaining tests declared non-significant regardless of their p-values. Endpoints and time points other than those above may have p-values reported, but none of these will be considered to be statistically significant.

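### Low priority: if the unstructured MMRM fails to converge, the only fallback is plain compound symmetry, which can make the SE at Week 13 and Week 52 too small or too large

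*SAP*

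**What the plan says.** SAP 7.3.2 fits the change in worst leg pain at Weeks 1, 2, 4, 6, 13, 26, 39 and 52 with an unstructured (UN) covariance and Kenward-Roger degrees of freedom. The contingency is one sentence: "Should the model fail to converge with the type = UN option, a compound symmetry structure will be used". Protocol 11.6.1 and the Synopsis carry the same sentence. Neither document asks for a refit with other starting values, a structure with visit-specific variances, or a robust SE. The only other convergence rule, in SAP 7.3.2.4, is for subgroups.

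The rule reaches beyond the primary test:

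- SAP 7.3.3.1 uses the same type of model for the key secondary endpoints, and notes that herniation "volume is collected only at Weeks 13 and 52; ODI assessment shares the same time points as the primary".
- In SAP 7.3.4, once the primary endpoint succeeds, "the treatment effect on the key secondary endpoint of worst leg pain score at Week 52 will be evaluated" next. That test then gates herniation volume and ODI.
- SAP 7.3.2.3 states: "The primary analysis and the key secondary analyses will be repeated on the PP population".
- SAP 7.3.2.2 states: "The MMRM analysis as described for the primary will be repeated for each of the 20 sets of data". SAP 7.3.3.2 extends the imputation approach to the key secondary endpoints.

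**The concern.** UN lets every visit have its own variance. Unqualified compound symmetry, named beside a SAS-style UN option, normally means the homogeneous form: one variance and one correlation for all visits. That it is homogeneous is an inference, since the documents do not use the word.

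Equal variances over a year of recovery cannot be taken for granted. Recovery at different speeds could spread the scores. A floor effect could narrow them: in the Japanese Phase 3 study, Protocol 1.2.2.1 reports that "The decrease in mean worst leg pain in the treatment groups also continued beyond Week 13". If variances differ, a single pooled variance gives the wrong SE at any visit whose own variance is not equal to the pooled one. Kenward-Roger adjusts inference within the assumed structure and does not repair it.

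At stake, only if the rule is triggered, are the SE of the primary test and the SE of the Week 52 leg pain test that comes second in the sequence.

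**Working it through.** **Inputs from the documents (SAP 2.6).** Difference 12 mm, "Common standard deviation (SD) of 30 mm", dropout 15%, power 90%, two-sided 5%, 160 per arm. No SD or correlation is given by visit.

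**The plan's own figure.** n per arm = 2 × 30² × (1.960 + 1.282)² / 12² = 131.3, so 132; 132/0.85 = 155.3, so 156 per arm and 312 in total. The t-test version gives 133, then 157 per arm and 314 in total. Both agree with the stated 320. With 160 × 0.85 = 136 per arm, SE = 30 × √(2/136) = 3.638, 12/3.638 = 3.298, and power = Φ(3.298 − 1.960) = 91.0%.

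**Number of covariance parameters.** UN: 8 × 9/2 = 36. Plain compound symmetry: 2. Heterogeneous compound symmetry: 8 + 1 = 9.

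**SE error under plain compound symmetry.** With complete data and visit-specific means, the fitted variance is the mean of the eight visit variances. Hence

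- ratio = model SE / true SE = pooled SD / visit SD
- actual two-sided type I error = 2 × (1 − Φ(1.96 × ratio))

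**Assumed visit SDs.** 30 mm at Week 13 and at most 35 mm at Week 52. As a plausibility check, Protocol 1.2.2.1 says of Week 52 that "the values were 30.9 mm in the placebo group and 18.5 mm in the 1.25 U dose group on a 100 mm VAS". A 0-100 score with mean m has SD at most √(m(100 − m)): 38.8 mm for 18.5 and 46.2 mm for 30.9, pooled 42.7 mm. So 35 mm is possible, but nothing in the documents shows that it is right.

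| Assumed SDs (mm), Week 1 to Week 52 | Week 13 | Week 52 |
|---|---|---|
| 30 throughout | 5.0% | 5.0% |
| 26/27/28/29, then 30 | 6.0% | 6.0% |
| 20/22/24/26, then 30 | 8.0% | 8.0% |
| 26/27/28/29/30/31/32/33 | 5.3% | 7.9% |
| 20/22/24/26/30/32/33/35 | 6.5% | 11.4% |
| 30 to Week 13, then 32/33/35 | 4.1% | 8.0% |
| 30 to Week 13, then 35 | 3.7% | 7.3% |
| 26/27/28/29/30/29/28/27 | 6.7% | 4.2% |
| 30 to Week 13, then 28/26/25 | 6.1% | 2.4% |

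Worked rows:

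- 20 to 35: variances sum to 6374; 6374/8 = 796.8; pooled SD 28.23. Ratios 28.23/30 = 0.941 (6.5%) and 28.23/35 = 0.806 (11.4%).
- 30, then 35: 8175/8 = 1021.9; pooled SD 31.97. Ratios 1.066 (3.7%) and 0.913 (7.3%). Week 13 power becomes Φ(3.298 − 1.96 × 1.066) = Φ(3.298 − 2.089) = 88.7%, against 91.0%.
- 30, then 28/26/25: 6585/8 = 823.1; pooled SD 28.69. Ratios 0.956 (6.1%) and 1.148 (2.4%).

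**With dropout.** Simulation of 2000 null trials per pattern, 160 per arm, 15% missing-at-random dropout, correlation 0.8 to the power of the log-week difference, REML; Monte Carlo SE 0.4-0.7 points. Over six of the patterns:

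| Method | Week 13 | Week 52 |
|---|---|---|
| Plain compound symmetry | 3.6-8.2% | 2.6-11.7% |
| Heterogeneous compound symmetry | 5.3-6.2% | 4.3-6.5% |
| Compound symmetry, sandwich SE | 4.3-5.1% | 4.2-6.4% |

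**Which replacement structures.** Large-sample fits under five assumed correlation shapes (constant 0.6; 0.85 to the power of visit lag; 0.3 + 0.7 × exp(−weeks/20); 0.8 and 0.7 to the power of the log-week difference) gave:

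- Heterogeneous compound symmetry: 5.0-5.9% at Week 13 and 2.7-5.0% at Week 52.
- Heterogeneous Toeplitz or AR(1): 1.5-5.0% and 0.8-7.4%. The worst case is the exponential shape, where both overstate the Week 13 SE by a factor of 1.24. Power is then Φ(3.298 − 1.96 × 1.24) = Φ(0.868), about 81%.

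**The case against.** The strongest reply is that this is a preference about a backup rule. The plan fixes the primary structure and one deterministic fallback, identically in both documents, and UN should converge with this sample size. That stands, and it is why the point has low priority.

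The reply that no document figure supports the sizes also stands. The high values need assumptions such as a Week 1 SD of 20 mm, and 11.4% also needs a rise to 35 mm at Week 52, although a floor effect is at least as plausible. The ranges are the extremes of chosen patterns. Other choices, with SDs up to 40 mm at Week 52, gave 3.6-8.8% at Week 13 and 1.9-11.7% at Week 52 with complete data, and about 15% at Week 52 with simulated dropout.

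The imputed-data fits are a partial safeguard. They are complete at every visit, so UN is least likely to fail there and would probably still give UN-based results. But they are sensitivity analyses under different missing-data assumptions and do not replace the primary test.

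Finally, heterogeneous compound symmetry is not uniformly better. In the simulation the sandwich SE was closer to 5% at Week 13, and plain compound symmetry was as good or better when SDs were nearly equal. The order of the two replacements is therefore a judgement. Putting heterogeneous compound symmetry first keeps Kenward-Roger, as the SAP already plans.

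**Conclusion.** The point holds as a low-priority improvement. If UN fails, the stated rule can give a wrong SE at Week 13 and Week 52, in a direction that the documents do not determine. In the patterns tried, the departures from 5% were larger at Week 52. Where the Week 13 SE is too large, the loss is small (91.0% to 88.7% power in the 3.7% pattern).

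A reader might infer that the planned primary test has an inflated type I error, or that 8.0% and 11.4% are its likely or maximum values. The documents support neither. The expected analysis is the UN model, which is unaffected. The fallback can be conservative as well as liberal, and equal SDs give exactly 5.0%.

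The conclusion rests on reading compound symmetry as homogeneous, on assumed visit SDs with 30 mm at Week 13, and on assumed correlation shapes. That non-convergence is unlikely is a judgement from 36 parameters and about 320 subjects; the documents give no estimate. The sample size is not in question.

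**What to change.** Replace the fallback sentence in SAP 7.3.2 and record the change in SAP section 11 before unblinding, so that no structure is chosen after a failure has been seen:

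> If the UN model fails to converge, it will be refitted with alternative starting values and then another parameterization (e.g. Cholesky). If it still fails, heterogeneous compound symmetry with Kenward-Roger will be used. If that fails, compound symmetry with an empirical (sandwich) SE and between-within degrees of freedom will be used.

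Apply this to the eight-visit leg pain and ODI models, including the PP and imputed-data fits. For herniation volume, with two visits, heterogeneous compound symmetry is the same three-parameter model as UN, so that step adds nothing there.

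Leave heterogeneous Toeplitz and AR(1) off the list. They index correlation by visit lag although the visits are unequally spaced, and they can cost more power than the rule being replaced.

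Cost: a few SAP lines and one entry in section 11, with no change to data or sample size. Some error remains if the correlation pattern is misspecified, as the five-shape results for heterogeneous compound symmetry show.
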